The Role of Acetazolamide in Mitigating Inflammation and Innate Immune Activation at High Altitude

Date of document: September 27, 2024

Title of Project: The role of acetazolamide in mitigating innate immune activation at high altitude: a randomized cross-over controlled trial

Executive Summary: High altitude exposure can lead to an acute pro-inflammatory response and activation of innate immune cells.¹⁻⁶ Our prior work demonstrates that 1 to 3 days at 3800 m elevation leads to increased expression of inflammatory damage associated molecular patterns (DAMPs), several toll-like receptor pathways involved in innate immune responses, as well as increases in pro-inflammatory monocyte and neutrophil subpopulations.^{1,6,7} Furthermore, our data and others indicate that either hypoxia-induced inflammatory responses, or baseline immune parameters, likely play a role in the onset and severity of Acute Mountain Sickness (AMS), although the precise mechanism is unknown.⁷ One of the most effective medical treatments for AMS is Acetazolamide (AZ).⁸ The mechanism of action by which AZ alleviates AMS is through regulation of blood bicarbonate levels, modification of blood pH, and resulting increases in ventilation and improved tissue oxygenation.⁸⁻¹⁰ However, AZ is also reported to have anti-inflammatory and immune-modulatory properties in animal models, which have not been evaluated as a potential mechanism of action in AMS treatment.^{11,12} We hypothesize that AZ will reduce pro-inflammatory responses and innate immune activation during 3 days of high-altitude exposure. To test this hypothesis, we will conduct a randomized, cross-over, placebo-controlled trial in which we administer AZ or placebo treatments to N=20 individuals over two visits to 3800 m elevation. Outcome measures will include the most detailed evaluation of systemic inflammatory and immune parameters to date in this field, as well as contributing physiological parameters including ventilatory chemoreflex sensitivity, and daytime and nocturnal pulse oximetry. This work will advance our knowledge about the pathology and treatment of a key wilderness medicine challenge by identifying a potential novel mechanism of AMS onset and treatment.

Section I – Summary

A. Introduction and Background: Acetazolamide (AZ) is a highly effective treatment for acute mountain sickness (AMS) at high altitude.^{8,9} AZ mitigates AMS through its activity as a renal carbonic anhydrase inhibitor, which decreases blood pH and stimulates ventilation to improve oxygen delivery to tissue.^{9,10} However, AZ also demonstrates immune modulatory properties, with most evidence examining this in lung tissue to investigate the impact on pulmonary hypertension in animal models.^{11,13} Our group and others show that high-altitude exposure results in an acute pro-inflammatory response and activation of the innate immune system, which some predict contributes to the onset and severity of AMS.^{1,7} Therefore, the anti-inflammatory properties of AZ may play a key role in modulating AMS symptoms independent of ventilatory stimulation. However, prior work has examined the impact of AZ on only a select few inflammatory mediators, and the impact of AZ on immune function has never been evaluated.

B. Hypothesis and specific aims: Our goal is to determine if AZ mitigates the pro-inflammatory innate immune response during high altitude travel. We hypothesize that AZ improves AMS symptoms, in part, by reducing systemic hypoxia-induced inflammation and reducing the activation of innate immune cells (monocytes and neutrophils). We will test this hypothesis with the following experimental aims: (**Aim 1**) Determine if AZ treatment during high altitude exposure blunts plasma inflammatory cytokine expression and levels of circulating pro-inflammatory innate immune cell subsets; (**Aim 2**) Determine if AZ treatment during high altitude exposure modulates immune cell function (innate inflammatory responses to bacterial and viral stimuli, cell migration, and bacterial killing efficacy).

C. Study design and methods:

a. Study Design: This is a double blind, randomized, cross-over, placebo-controlled trial.

Participants (N=20) will be recruited by word of mouth and advertising, and complete written

informed consent in the UC Riverside laboratory within 1 month of first ascent (Summer 2025). Participants then complete medical history and basic physical screening. At this time, they are randomly assigned to a treatment group (*i.e.* Group A taking AZ on trip 1 and placebo on trip 2), maintaining age and sex ratios across groups. Participants will be asked to begin taking their assigned treatment as indicated 2 days before each ascent (125 mg twice daily for AZ).¹⁴ On the morning of ascent, participants arrive at the lab at 6:00 am and fasting peripheral venous blood samples will be collected by a licensed phlebotomist or physician. Participants then travel to Barcroft Station (3800 m elevation) *via* vehicle (6 -7 hours). Over three days at high altitude, participants complete morning fasting blood draws, morning and evening AMS questionnaires (Lake Louise)¹⁵, and morning and evening physiological measures (blood pressure, heart rate, SpO₂). On the second day at high altitude, ventilatory chemoreflex measures will be collected as previously described by our group.¹⁶ WatchPAT sleep kits will be used to characterize nocturnal hypoxic burdens, oxygen desaturation indices, and apnea hypopnea indices as previously described by our group.¹⁷ Following descent, participants complete 1-week and 1-month follow-up visits to determine the long-term effects of high-altitude exposure on immune phenotypes.

100 µl of whole blood will be fixed and stained immediately on-site at each timepoint for flow cytometry analysis at UC Riverside within 3 days of sample collection. We will also conduct complete blood counts on-site. 20 ml of EDTA-treated blood will be utilized for plasma collection and isolation of peripheral blood mononuclear cells by density gradient centrifugation. Isolated immune cells will be immediately frozen and stored in liquid nitrogen for transport to UC Riverside using a novel protocol optimized by our group for cryogenically storing viable cells in remote field locations.⁷ Upon return to sea level, immune cells will be cultured in the presence or absence of several stimulants including bacterial lipopolysaccharide (LPS) and R848 (Resiquimod, stimulating the antiviral response). Following stimulation, we will collect culture

supernatants and measure expression of inflammatory factors using Legendplex multi-plex cytokine panels as previously described by our group.¹⁸ These panels allow simultaneous measurement of many key inflammatory mediators including 13 inflammatory cytokines, 12 markers of vascular inflammation, and 13 anti-viral response factors. We will also conduct additional functional assays, including bacterial killing and cell migration assays. Plasma cytokine levels will also be measured via Legendplex. All cell culture assays will be conducted in triplicate with downstream cytokine profiling in duplicate.

b. Power calculations: Sample sizes are based on power calculations targeting 80% power to detect significant differences across sea level and high altitude at $\alpha = 0.05$. Calculations were performed using *pwr* in R and are based on previously published data or our own preliminary work. A sample size of 14 is required to detect a significant shift from classical to intermediate monocyte subsets after 1 day at high altitude with an effect size in our prior studies of 0.46.⁷ Additionally, a sample size of 10-36 is required to detect significant correlations between AMS score and classical ($R^2 = 0.79$) or non-classical monocytes ($R^2 = 0.45$). Finally, we previously identified elevations in inflammatory response genes after 1-3 days at high altitude with a sample size of 17.¹ Thus, we predict we are well powered with a sample size of 20 individuals (cross-over design) to detect significant changes in immune phenotypes at high altitude as well as correlations between immune cell distributions and AMS scores. This sample size is also consistent with other studies examining the efficacy of AZ for AMS treatment.¹⁹

c. Data analysis plan: Treatments will be assigned by a third party and all study team members and participants will be blinded. Data analysis will be conducted by a research team member who is blinded to participant treatment, demographic information, and day of sample collection. All samples and physiological data will be deidentified and coded. To determine if AZ treatment is linked to reduced inflammatory cytokine expression and reduced levels of pro-inflammatory

innate immune cell subsets (Aim 1), we will first utilize two-way repeated measures ANOVA to compare plasma cytokine expression and cell distributions across study days and treatments. To determine the impact of AZ treatment on innate immune cell function (Aim 2), we will use a three-way ANOVA to examine cell cytokine secretion across study days, treatments, and pre/post cell stimulation. Significant main effects will be further evaluated with post-hoc Tukey's HSD tests, and we will verify our data meets all required test assumptions. We will carefully examine impacts of sex, age, BMI and other demographic factors on outcomes using mixed linear models. WatchPAT data will be analyzed according to the American Academy of Sleep Medicine criteria by a qualified sleep technician and ventilatory parameters will be analyzed as described previously.^{16,20–22} To determine if these parameters are associated with our immune and AMS outcomes, we will conduct mixed linear models with trip, day, treatment, and sex, as covariates.

d. Timeframe: This study will take place in the summer of 2025. Participants will be recruited in the month prior to study start, and work will be conducted over two expeditions. Participants will complete baseline testing within one week of ascent. They will then arrive on the morning of ascent for sea-level blood sampling, be driven to Barcroft Station over 6 hours in vans, and will remain at the station for 3 nights (4 days) during each visit. The group will then return to sea level and a follow-up appointment will be completed 1 week and 1 month following return. The second trip will take place 1-2 months after the first. Flow cytometry and multiplex cytokine panel tests will be conducted immediately after each trip, and cell functional assays will be completed within 2 months of return. Final data analyses will be complete over the following 2 months in time for an abstract submission to the American Physiology Summit by the deadline in Fall 2025 and attendance of the 2026 Winter Conference of the Wilderness Medical Society. The manuscript resulting from this work will be submitted for publication in *Wilderness & Environmental Medicine* by Summer 2026.

e. Facilities: This study will be performed at the UC Riverside School of Medicine and Barcroft Station in the White Mountain Research Center. Barcroft Station is located approximately 6 hours northeast of UC Riverside and our team has extensive experience at this site. The facilities house up to 20 participants in dormitory-style lodging, provides three meals per day, and contains separate laboratory spaces in for blood sample processing and cell collection. Our facilities at UC Riverside include a large, biosafety level 2 laboratory space with separate space for studies with human subjects. We have access to all necessary equipment to this work including a NovoCyte Quanteon Flow Cytometer, biosafety cabinets and incubators, centrifuges, fridges and freezers, and cryogenic storage for cells.

D. Institutional Review Board approval: Approval for this study has been granted by the UC Riverside IRB (project #HS-22-088). An amendment will be required to add the AZ treatment, and will be submitted for approval immediately following notice, if we are funded.

E. Clinical Trial Registration: This study will be registered at ClinicalTrials.gov prior to the start of data collection and recruitment. We will work with our UC Riverside Clinical Trial Coordinator, [name], to verify we meet all regulatory requirements.

F. Significance: This work aligns with the mission of WMS to improve our scientific knowledge of human health activities in a wilderness environment. It will provide a novel mechanism by which AZ mitigates AMS and may lead to new therapeutic approaches. Furthermore, we will generate new knowledge regarding the precise ways in which high altitude exposure influences immune function which has implications for understanding the impact of hypoxemia and physiological stress on infectious disease susceptibility. This work may also indicate a novel role for immune activation in AMS development.

Section II – References

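### No acetazolamide–placebo outcome is named primary, and Tukey's HSD does not control false treatment effects across the multiplex analytes and cell subsets

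*Protocol*

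**What the plan says.** Protocol Section I, C.a describes the multiplex panels used on culture supernatants: "13 inflammatory cytokines, 12 markers of vascular inflammation, and 13 anti-viral response factors". On plasma it says only "Plasma cytokine levels will also be measured via Legendplex", without naming panels. Aim 1 (Section I, B) adds circulating innate cell subsets, and their number is not given.

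Section I, C.c sets the tests. For Aim 1, "we will first utilize two-way repeated measures ANOVA to compare plasma cytokine expression and cell distributions across study days and treatments". For Aim 2, a "three-way ANOVA to examine cell cytokine secretion across study days, treatments, and pre/post cell stimulation". Analyte is not a factor in either model, so this means one ANOVA per outcome. The only multiple-comparison step is: "Significant main effects will be further evaluated with post-hoc Tukey's HSD tests".

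The only significance level in the document is 0.05. It stands in C.b, where the power target is for differences between sea level and altitude. No outcome is called primary. Section I, F says of the work: "It will provide a novel mechanism by which AZ mitigates AMS".

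**The concern.** Both aims ask whether AZ changes something, but nothing says which result answers either question. A reader of C.c could take Tukey's HSD to be the plan's protection against multiple testing. It adjusts comparisons between levels of a factor within one ANOVA. It does not adjust for looking at many analytes in turn, which is where most of the multiplicity lies.

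At stake is how a handful of nominally significant cytokines would be read. With no primary outcome and no control across analytes, they could be reported as evidence of an anti-inflammatory mechanism, although a few such results are expected if AZ has no effect on any analyte.

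**Working it through.** **The plan's own figure.** The protocol states no familywise error rate. The nearest figure is n = 14 for the monocyte shift, with effect size 0.46, 80% power and alpha 0.05 (C.b). A one-way ANOVA power formula with f = 0.46 and k = 4 groups gives 14 per group, power 0.803. The value k = 4 (sea level plus three altitude days) is assumed, because the type of effect size is not stated. A paired t test with d = 0.46 would instead need 40, two-sided. By C.b's own description the figure concerns altitude against sea level, so it neither singles out nor powers an AZ contrast.

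**Inputs.**
- Culture analytes: 13 + 12 + 13 = 38 (C.a).
- Plasma analytes: not stated. The range runs from 13 (inflammatory panel only) to 38 (all three panels).
- Level: 0.05, two-sided (level from C.b; sidedness and use for each analyte assumed).
- One treatment test per analyte, with no true AZ effect on any of them.

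**Does Tukey's HSD help the AZ contrast?** There are two treatment levels. With 20 participants and 19 degrees of freedom, the Tukey critical value on the t scale is q(0.95; 2, 19)/√2 = 2.093. The unadjusted two-sided t value is t(0.975; 19) = 2.093. They are the same, so it does not.

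**Expected false treatment effects** (m × 0.05, whatever the correlation):
- m = 38: 38 × 0.05 = 1.9
- m = 13: 13 × 0.05 = 0.65

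**Chance of at least one, independent tests** (1 − 0.95^m):
- m = 38: 1 − 0.95^38 = 0.858
- m = 13: 1 − 0.95^13 = 0.487

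**Chance of at least one, correlated tests.** With common correlation ρ and a standard normal common factor C, the chance is 1 − E[{Φ((1.96 − √ρ·C)/√(1−ρ)) − Φ((−1.96 − √ρ·C)/√(1−ρ))}^m], averaged over 200,000 draws of C.

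| ρ | m = 38, common ρ | m = 38, ρ within the three panels only | m = 13, common ρ |
|---|---|---|---|
| 0.3 | 0.73 | 0.80 | 0.42 |
| 0.5 | 0.56 | 0.70 | 0.33 |
| 0.7 | 0.37 | 0.56 | 0.24 |
| 0.9 | 0.18 | 0.36 | 0.14 |

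Cell subsets are left out because their number is not stated. Five, as an illustration, would make 43 tests: 43 × 0.05 = 2.15 expected, and 1 − 0.95^43 = 0.890 if independent.

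**What 20 pairs can detect.** From the noncentral t with 20 complete pairs and 80% power, the detectable standardized paired difference is about 0.66 at two-sided 0.05. At 0.05/38 = 0.0013 it is about 1.05.

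**The case against.** The strongest reply is that error control over a biomarker panel is commonly left to a statistical analysis plan, which may exist and is not shown. If C.c were silent on multiplicity, that would settle this part. C.c is not silent: it picks a procedure, and that procedure does not act across outcomes. Naming the outcome that answers the aim is also a protocol matter.

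Several stronger readings are tempting and are not supported:

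- A reader might infer that 38 analytes are tested in plasma. The panel counts are given for culture supernatants. With 13 plasma cytokines, a false effect is slightly less likely than not even under independence (49%).
- A reader might count interactions as well and reach 76 tests and 98%. C.c sends only main effects to follow-up. Nor should each culture condition count as a separate test, because stimulation is a factor in the Aim 2 model.
- A reader might take it that one significant cytokine is enough to establish the mechanism. No such rule is written. The Section F sentence is a statement of significance, and the Executive Summary speaks only of a potential mechanism.
- The hypothesis is directional: AZ should reduce inflammation. Only false effects in that direction would seem to support it. For 38 tests that is 38 × 0.025 = 0.95 expected and 1 − 0.975^38 = 0.62 if independent; for 13 tests the chance is 1 − 0.975^13 = 0.28.
- A reader might regard the intermediate monocyte shift as an AZ endpoint already powered. C.b sizes it as an altitude effect, beside AMS correlations and earlier gene-expression work.

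These points narrow the size of the problem. They leave standing that no primary AZ contrast is named and that Tukey's HSD gives it no protection.

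**Conclusion.** The point holds in a limited form. The protocol names no primary AZ–placebo outcome, and the correction it chooses does not control error across analytes and cell subsets. For the 38 culture analytes, 1.9 false treatment effects are expected under no effect. The chance of at least one runs from 86% (independent) through about 56% (common correlation 0.5) to 18% (0.9). For plasma it depends on panels not named: 0.65 expected and 49% if independent with the 13-cytokine panel alone.

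This rests on one two-sided test per analyte at 0.05, which is inferred from the only level in the document. Whether a false finding is more likely than not depends on the correlation between analytes, which the protocol does not give. Even the lowest figure for the 38 analytes is more than three times 5%.

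**What to change.** In Section I, C.c:

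1. Apply Benjamini-Hochberg at 5% to the treatment-effect p-values, one per analyte, across the plasma analytes, and separately across the Aim 2 culture analytes. Name the plasma panels so that the first family is defined. Label results that do not survive as exploratory, and say whether the cell subsets other than the primary are exploratory too.
2. Name one primary AZ–placebo contrast for Aim 1, tested at two-sided 0.05. The intermediate monocyte fraction at altitude is one candidate; the sponsor may prefer another.
3. In C.b, state that n = 14 concerns the altitude shift and does not power that contrast. Give the power basis for the contrast chosen: with 20 complete pairs, about 0.66 standard deviations of the paired difference is detectable at 80% power. Dropout would raise this.

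No added samples or assays are needed for step 1. The price is lower power for individual cytokines. The strictest Benjamini-Hochberg cut-off over 38 analytes is 0.05/38, where the detectable difference is about 1.05 rather than 0.66; the loss is smaller when several analytes respond together. Steps 2 and 3 need more than wording, because the sponsor must judge whether a difference of about 0.66 is plausible for the chosen outcome.

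### The power section gives no figure for acetazolamide versus placebo, and its stated sizes (14 and 10-36) do not match the contrasts and labels attached to them

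*Protocol*

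**What the plan says.** Protocol, Section I, C.b (Power calculations) sets the target: "Sample sizes are based on power calculations targeting 80% power to detect significant differences across sea level and high altitude". On method it says "Calculations were performed using *pwr* in R and are based on previously published data or our own preliminary work"; it does not name the function, the number of groups or the sidedness.

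Three supports follow:
- A monocyte shift: "A sample size of 14 is required to detect a significant shift from classical to intermediate monocyte subsets after 1 day at high altitude". The figure used for this is 0.46, taken from the group's earlier work.
- Correlations: "a sample size of 10-36 is required to detect significant correlations between AMS score and classical" (R² given as 0.79) or non-classical monocytes (R² given as 0.45).
- An earlier altitude gene-expression study with 17 participants.

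The section concludes: "we predict we are well powered with a sample size of 20 individuals (cross-over design) to detect significant changes in immune phenotypes at high altitude", and extends this to correlations between immune cells and AMS score. Its only remark about treatment is that 20 is in line with other studies of AZ for AMS.

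The Executive Summary states what the trial is for: "We hypothesize that AZ will reduce pro-inflammatory responses and innate immune activation during 3 days of high-altitude exposure". Section I, B frames both aims around the effect of AZ treatment. Section I, C.c plans ANOVAs with treatment as a factor: day by treatment for Aim 1, and day by treatment by stimulation for Aim 2.

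**The concern.** A randomised, placebo-controlled cross-over should justify its size for the randomised comparison. Here every calculation concerns either the change from sea level to altitude or a correlation. Neither tells a reader how large an AZ effect the trial can detect, and that reader needs the figure to interpret a null result.

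The two sets of calculated sizes also look out of step with their descriptions. A size of 14 is small for a two-time-point comparison at 0.46. A requirement of up to 36 sits beside a claim that 20 is enough.

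**Working it through.** **Inputs (Section I, C.b).** Power 80%, α = 0.05 (two-sided assumed; the protocol does not say), effect size 0.46 (metric not stated), stated n = 14, R² = 0.79 and 0.45 with stated n = 10-36, planned N = 20.

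**1. The stated 14.**

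*Paired t-test.* Power = P(|T| > t₀.₉₇₅,ₙ₋₁), with T noncentral t on n−1 df and noncentrality d√n. With d = 0.46:
- n = 14: power 36%
- n = 20: power 50%
- n = 39: 79.9%; n = 40: 81.0%, so 40 are needed (solution 39.06)

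*One-way ANOVA, independent groups.* Noncentral F on k−1 and k(n−1) df, λ = k·n·f². With f = 0.46:

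| Groups k | n per group for 80% |
|---|---|
| 2 | 19.6, so 20 |
| 3 | 16.2, so 17 |
| 4 | 13.9, so 14 |
| 5 | 12.3, so 13 |

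The named contrast has two time points (sea level and day 1). Neither the paired d nor the two-level f gives 14. Four groups do, which would fit sea level plus three altitude mornings tested as an omnibus with independent groups.

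*Other routes to 14.* With within-person correlation ρ, the paired effect is d/√(2(1−ρ)). If 0.46 is a raw d, ρ of about 0.84 gives 14. If it is f (two-level d = 2 × 0.46 = 0.92), ρ of about 0.36 gives 14. Treating 0.46 as an R² in a correlation test gives 13.9. The protocol states none of these.

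**2. The stated 10-36.** The approximation used by *pwr* is: power ≈ Φ((z_r − z_c)√(n−3)), with z_r = atanh(r) + r/(2(n−1)) and z_c = atanh of the critical r.

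| Value | Read as r: n | Read as R²: n |
|---|---|---|
| 0.79 | 9.3, so 10 | r = √0.79 = 0.889: 6.5, so 7 |
| 0.45 | 35.6, so 36 | r = √0.45 = 0.671: 14.3, so 15 |

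The printed 10 and 36 match r, not R². At N = 20, power is 99% for r = 0.79 and 53% for r = 0.45. If 0.45 really is R², power is 93%.

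**3. The contrast that is missing.** For AZ versus placebo with 20 completers, solving the paired-t power for 80% gives a standardised within-person difference of 0.66 (also 0.66 with n−2 df to allow for a period effect). This uses only n and α, and nothing about 0.46. With 18 completers it is 0.70, and with 16 it is 0.75.

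**4. What this means for blunting.** Assumption: the AZ-placebo difference in the altitude response has the same SD as the altitude shift itself, which holds if a person's two altitude responses correlate at 0.5. The paired effect is then the blunted fraction times the altitude effect. Power at n = 20:

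| Altitude effect blunted | 0.46 is a paired d | 0.46 is f, paired d = 0.92 (ρ = 0.5) |
|---|---|---|
| 100% | 0.46: 50% | 0.92: 97% |
| 75% | 0.345: 31% | 0.69: 83% |
| 50% | 0.23: 16% | 0.46: 50% |

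The protocol does not say which column applies.

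**The case against.** Four points can be made for the protocol, and each limits the finding.

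*It never claims power for AZ.* This stands. The concluding sentence covers altitude changes and correlations only. A reader might infer a false claim about the treatment effect, but the text does not make one. The gap is an omission, in a section that nonetheless presents 20 as the justified size of the trial. Nor are the altitude and correlation questions foreign to the trial: study day is a factor in the ANOVAs, and associations between physiological parameters and immune and AMS outcomes are planned.

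*The 14 may be a correct software result.* This also stands. It is what *pwr* returns for four groups at f = 0.46, and unstated correlations could also produce it. A reader might call it an arithmetic error. The document does not support that, because it gives neither the metric nor the test.

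*The low powers for blunting are one reading.* Correct. Quoting 50%, 31% and 16% alone would show only the pessimistic end, and if f = 0.46 is the true metric, full or 75% blunting is well covered. It is also tempting to say that AZ can at most remove the altitude effect. The protocol does not say so: treatment starts two days before ascent, and Aim 2 speaks of modulation.

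*The size agrees with other AZ trials.* That remark concerns AMS as the outcome, not the immune measures of Aims 1 and 2, and it is not a calculation. It does not fill the gap.

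The protocol states no rule for reading a null result, so one cannot say that a null would be misread, only that the figure needed to read it is absent.

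**Conclusion.** The point holds in this form. N = 20 is justified for sea level versus altitude and for AMS correlations, and nothing is given for the randomised contrast. The detectable paired AZ-placebo difference is 0.66 SD, assuming 20 completers and a two-sided 0.05 test of a single outcome. Whether that is adequate cannot be settled from the protocol: under the same-SD assumption, power to detect a halving of the altitude effect is 16% to 50%, depending on what 0.46 means.

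The 14 is mismatched to its named contrast, and its effect-size metric is undefined.

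The correlation statement is inconsistent in itself: a requirement of up to 36 cannot support a claim of adequate power at 20 across the stated range. Either the values are r, and the weaker correlation has 53% power, or they are R², and the printed sizes should be about 7 and 15.

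**What to change.** In Section I, C.b:

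1. Add a sentence for the randomised contrast: 20 completers in the cross-over give 80% power (two-sided α 0.05) for a paired AZ-placebo difference of 0.66 SD of the within-person difference. If power for blunting is also quoted, give it as a range with its assumptions.
2. State whether 0.46 is d, f or another measure, which test and how many time points were used, and any within-person correlation. Restate the 14 to match: 40 if it is a paired d; if it is f from a four-group one-way ANOVA, say so, give 14 as per group, and drop the day-1 description.
3. Correct the R²/r labels. If 0.79 and 0.45 are r, confine the claim of adequate power for correlations to the stronger one (classical monocytes). If they are R², replace 10-36 with 7-15.

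The cost is protocol wording and a less favourable stated figure. No participants, visits or assays are added.

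### The 10-36 sample-size range for the AMS-monocyte correlations does not follow from the R² values printed beside it, and its upper end of 36 is at odds with the conclusion that 20 participants suffice

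*Protocol*

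**What the plan says.** Protocol Section I, C.b (Power calculations) sets the target: "Sample sizes are based on power calculations targeting 80% power", with alpha 0.05 and no statement of one- or two-sided testing. On the tool and the inputs it says: "Calculations were performed using *pwr* in R and are based on previously published data or our own preliminary work".

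For the link between AMS score and monocyte subsets it states that "a sample size of 10-36 is required to detect significant correlations between AMS score and classical ($R^2 = 0.79$) or non-classical monocytes", with R² = 0.45 printed for the non-classical subset.

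The paragraph then concludes: "Thus, we predict we are well powered with a sample size of 20 individuals (cross-over design"), and it extends this adequacy to immune phenotype changes "as well as correlations between immune cell distributions and AMS scores". It does not explain how 20 meets a requirement whose upper end is 36.

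**The concern.** Two things in the paragraph do not fit.

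- **Effect sizes and range.** A correlation with R² = 0.45 is strong (r about 0.67), and 36 participants is far more than such a correlation needs.
- **Range and conclusion.** The stated upper requirement exceeds the planned enrolment by 36 − 20 = 16, yet the text calls the study well powered for these correlations without limiting the claim to one subset.

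The correlations are one of the supports offered for N = 20. As the text stands, a reader cannot tell whether a simple correlation of AMS score with non-classical monocytes has about 93% or about 53% power, and so cannot judge how informative a null result would be.

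**Working it through.** **Inputs from C.b.** Alpha 0.05; power 80%; *pwr* in R; values 0.79 (classical) and 0.45 (non-classical), both labelled R²; stated requirement 10-36; planned N = 20. **Assumption:** two-sided testing, since sidedness is not stated.

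**Formulas.** The correlation routine in *pwr* was re-coded:
- critical correlation r_c = √(t² / (t² + n − 2)), where t is the 97.5% point of the t distribution on n − 2 degrees of freedom;
- power ≈ Φ((z_r − z_c)·√(n − 3)), where z_r = atanh(r) + r/(2(n − 1)) and z_c = atanh(r_c); the opposite tail is included but negligible.

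As a hand check, the plain Fisher approximation is n = ((1.960 + 0.842)/atanh(r))² + 3.

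**Step 1: reproduce the stated range, and compare it with the range as labelled.**

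| Value entered | r | atanh(r) | n, pwr routine | n, plain Fisher | Rounded up (pwr) |
|---|---|---|---|---|---|
| 0.79 as r | 0.790 | 1.071 | 9.31 | 9.84 | 10 |
| 0.45 as r | 0.450 | 0.485 | 35.62 | 36.41 | 36 |
| 0.79 as R² | 0.889 | 1.416 | 6.51 | 6.91 | 7 |
| 0.45 as R² | 0.671 | 0.812 | 14.26 | 14.90 | 15 |

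Both ends of the printed range come out exactly when the values are entered as r. Neither does when they are read as R².

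**Step 2: look for another route to 10-36.**
- One-sided testing gives 8 and 29 with the values as r, and 6 and 12 with them as R².
- With 0.45 read as R², a power of 90% or 95% gives 18.3 or 22.0. An alpha of 0.025, 0.0167 or 0.01 gives 16.9, 18.4 or 20.4. A regression F-test with f² = R²/(1 − R²) and one to five predictors gives 11.9 to 21.9.

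None of the R² variants tried exceeds about 22, so none explains 36.

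**Step 3: power at n = 20, one pair per person.** Here t = 2.101, r_c = 0.444, z_c = 0.477 and √17 = 4.123.
- r = 0.45: z_r = 0.4847 + 0.45/38 = 0.4965; (0.4965 − 0.4769) × 4.123 = 0.081; power 53.2% (simulation 53.2%).
- R² = 0.45 (r = 0.671): z_r = 0.8122 + 0.671/38 = 0.8299; (0.8299 − 0.4769) × 4.123 = 1.455; power 92.7% (simulation 93.0%).
- r = 0.79: 99.4%. R² = 0.79: above 99.9%.

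The smallest |r| detectable with 80% power at n = 20 is 0.58 (R² about 0.34).

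**The case against.** The best defence is that the printed effect size should be taken at its word. If 0.45 is R², the requirement is 15, power at n = 20 is about 93%, and the conclusion is right. Only the intermediate range is wrong, and it errs on the cautious side. This stands. A reader might infer from 36 against 20 that the trial fails to deliver its 80% power and that the non-classical test is close to a coin flip. The protocol does not support that as a general statement: it is true only if the R² label is the mistake, and the prior data that would settle this are not given.

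A second defence is the cross-over. Section C.a plans daily blood draws and twice-daily AMS scores on each of two trips, so one pair per person is not all the information available. This stands in part. Two trips by 20 people do not give 40 independent pairs, which is what the routine assumes, but a repeated-measures analysis may do better than 53%. As an illustration, assume one pair per trip, a correlation of 0.45 both within and between persons, and the same intraclass correlation (ICC) for both variables. None of these assumptions comes from the protocol. The effective number of pairs is then 40/(1 + ICC²), or about 37, 32 and 27 for ICC 0.3, 0.5 and 0.7, with power of about 81%, 75% and 67%. A generalised least squares analysis with known ICC reached roughly 85% in simulation. A treatment effect, or a weaker within-person correlation, would lower these figures. So it would be too strong to say that the cross-over cannot help. The protocol, however, offers no such calculation and mentions the cross-over only in parentheses.

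A third defence is that neither aim in Section B is an AMS-monocyte correlation. This is correct, and it limits the severity. It does not remove the error, because the range and the conclusion are both stated in the protocol.

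**Conclusion.** The point holds as an internal inconsistency of moderate severity. The printed range matches 0.79 and 0.45 used as r, while the text calls them R², and the upper figure of 36 is not reconciled with 20 participants. No reading leaves the paragraph correct as written:

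- **Values are R²:** the range should be 7-15. The conclusion stands, with power at n = 20 above 99% and about 93%.
- **Values are r:** the label is wrong. The claim holds for classical monocytes (10 needed, power about 99%). For non-classical monocytes, 36 are needed, and a simple correlation with one pair per person has about 53% power at n = 20.

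These figures assume two-sided alpha 0.05, a bivariate correlation and no loss of participants. It does not follow that the trial is underpowered for its aims. Nor does the protocol say that a null correlation would be taken as evidence of no association.

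**What to change.** Check the prior data to establish whether 0.79 and 0.45 are r or R², then amend C.b accordingly.

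- **If R²:** replace the range with 7-15 and keep the conclusion.
- **If r:** correct the label. State that non-classical monocytes need 36 against 20 enrolled, and that a simple correlation with one pair per person has about 53% power. Drop the well-powered claim for that correlation unless a calculation that allows for repeated measures on the same 20 people supports it.

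State that the calculation is two-sided, if it is. Optionally, add that n = 20 detects |r| of about 0.58 with 80% power.

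The cost is the rewording of one paragraph, with no change to design, enrolment or procedures. The only downside is that a stated figure may become less favourable.
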